3.2.4 Other efficacy outcome endpoints

3.2.4.1 Time to first subsequent therapy or death (TFST)

As a supportive summary to PFS, time to first subsequent therapy or death (TFST) is defined as the time from the date of randomisation to the earlier of start date of the first subsequent anti-cancer therapy after discontinuation of randomised treatment, or death (i.e. date of first subsequent anti-cancer therapy/death or censoring – date of randomisation + 1). Any patient not known to have had a first subsequent anti-cancer therapy or have not died at the time of the analysis will be censored at the last date that the patient was known not to have received a first subsequent anti-cancer therapy (obtained from the TTSCAPRX form). If a patient terminated the study for reason other than death before first subsequent therapy, these patients will be censored at the earliest of their last known to be alive and termination dates. Patients not receiving randomised treatment would have TFST calculated in the same way, i.e. time from date of randomisation to the initial subsequent therapy or death. Any participant without a TTSCAPRX form (not known to have had a first subsequent anti-cancer therapy) and have not died at the time of the analysis is censored at the last date that the participant was known to be alive, where any participant recorded as alive or to have died after DCO date is censored at the date of DCO.

3.2.4.2 Time to second subsequent therapy or death (TSST)

As a supportive summary to PFS2, time to second subsequent therapy or death (TSST) is defined as the time from the date of randomisation to the earlier of start date of the second subsequent anti-cancer therapy after discontinuation of first subsequent treatment, or death (i.e. date of second subsequent anti-cancer therapy/death or censoring – date of randomisation + 1). Any patient not known to have had a second anti-cancer subsequent therapy or have not

died at the time of the analysis will be censored at the last date that the patient was known not to have received a second subsequent anti-cancer therapy (obtained from the TTSCAPRX form). If a patient terminated the study for reason other than death before second subsequent therapy, these patients will be censored at the earliest of their last known to be alive and termination dates. Patients not receiving randomised treatment would have TSST calculated in the same way, i.e. time from date of randomisation to the second subsequent therapy or death. Any participant without a TTSCAPRX form (not known to have had a second subsequent anti-cancer therapy) and have not died at the time of the analysis is censored at the last date that the participant was known to be alive, where any participant recorded as alive or to have died after DCO date is censored at the date of DCO.

3.3 Safety variables

Safety and tolerability will be assessed in terms of AEs (including serious AEs [SAEs]), deaths, laboratory data, vital signs, electrocardiograms (ECGs) and exposure. These will be collected for all patients.

Unless otherwise specified, ‘on-treatment’ will be defined as assessments between date of the first dose and 90 days following last dose of the IP (durvalumab/placebo) or initiation of the first subsequent anti-cancer therapy (excluding palliative radiotherapy), whichever occurs first.

3.3.1 Adverse events

AEs and SAEs will be collected throughout the study, from date of the patient signing the ICF of study procedure (part II screening) until 90 days after the last dose of study treatment. Events will be defined as treatment emergent if they onset, or worsen (by investigator report of a change in intensity), during the treatment period as defined in the protocol. The Medical Dictionary for Regulatory Activities (MedDRA) (using the latest or current MedDRA version) will be used to code the AEs. AEs will be graded according to the National Cancer Institute Common Terminology Criteria for AEs (CTCAE Version 5.0).

AEs of special interest and AEs of possible interest

Some clinical concepts (including some selected individual preferred terms and higher level terms) have been considered “AEs of special interest” (AESI) and “AEs of possible interest” (AEPI) to the durvalumab program.

The AESIs reported in the AstraZeneca-sponsored durvalumab studies are defined as AEs with a likely inflammatory or immune-mediated pathophysiological basis resulting from the mechanism of action of durvalumab and requiring more frequent monitoring and/or interventions such as corticosteroids, immunosuppressants, and/or endocrine therapy. Endocrine therapies include standard endocrine supplementation, as well as treatment of symptoms resulting from endocrine disorders (for example, therapies for hyperthyroidism include beta blockers [e.g., propranolol], calcium channel blockers [e.g., verapamil, diltiazem], methimazole, propylthiouracil, and sodium perchlorate).

The AEPIs reported in the AstraZeneca-sponsored durvalumab studies are defined as AEs that could have a potential inflammatory or immune-mediated pathophysiological basis resulting from the mechanism of action of durvalumab but are more likely to have occurred due to other pathophysiological mechanisms, thus, the likelihood of the event being inflammatory or immune-mediated in nature is not high and/or is most often or usually explained by the other causes.

These AESIs and AEPIs have been identified as

Pneumonitis, Hepatic events, Diarrhea/Colitis, Intestinal perforations, Adrenal Insufficiency, Type 1 diabetes mellitus, Hyperthyroid events, Hypophysitis, Hypothyroid events, Thyroiditis, Renal events, Dermatitis/Rash, Pancreatic events, Myocarditis, Myasthenia gravis, Guillain-Barre syndrome, Myositis, Infusion/hypersensitivity reactions, Other rare/miscellaneous. Other categories may be added or existing terms may be merged as necessary. An AstraZeneca medically qualified expert after consultation with the Global Patient Safety Physician has reviewed the AEs of interest and identified which preferred terms contribute to each AESI/AEPI. A further review will take place prior to Database lock (DBL) to ensure any further terms not already included are captured within the categories.

Immune-mediated Adverse Events (imAEs)

imAEs will be identified from both AEs of special interest (AESIs) and AEs of possible interest (AEPIs) based on programmatic rules that consider interventions involving systemic steroid therapy, immunosuppressant use, and/or endocrine therapy (which, in the case of AEPIs, occurs after first considering an Investigator’s causality assessment and/or an

Investigator's designation of an event as immune-mediated). Endocrine therapies include standard endocrine supplementation, as well as treatment of symptoms resulting from endocrine disorders (for example, therapies for hyperthyroidism include beta blockers [e.g., propranolol], calcium channel blockers [e.g., verapamil, diltiazem], methimazole, propylthiouracil, and sodium perchlorate). Further details are provided in the imAE charter.

In addition, the Sponsor may perform medical review of those AESIs and classify them as imAEs or not imAEs via an independent manual adjudication process.

Confirmed/Suspected COVID-19 infection

Confirmed/suspected COVID-19 infection is defined as an AE with preferred term within the AE search criteria developed by the latest MedDRA MSSO guidance for COVID-19.

3.3.2 Laboratory data

Laboratory data will be collected throughout the study, from Part II screening to follow-up visit as described in the CSP. Blood and urine samples for determination of haematology, clinical chemistry, and urinalysis will be collected as described in section 8.2.1 of the CSP. For the definition of baseline and the derivation of post baseline visit values considering visit window and how to handle multiple records, derivation rules as described in [section 4.1.3](#) below will be used.

Change from baseline in haematology and clinical chemistry variables will be calculated for each post-dose visit on-treatment. CTCAE grades will be defined at each visit according to the CTCAE grade criteria using local or project ranges as required, after conversion of lab result to corresponding preferred units. The following parameters have CTCAE grades defined for both high and low values: Potassium, Sodium, Magnesium, Glucose and Corrected calcium.

Corrected calcium will be derived during creation of the reporting database using the following formula:

$$\text{Corrected calcium (mmol/L)} = \text{Total Calcium (mmol/L)} + ([40 - \text{Albumin (G/L)}] \times 0.02)$$

Creatinine clearance (CrCl) (mL/min) will be derived according to the Cockcroft-Gault formula ([Cockcroft and Gault 1976](#)), where the most recent weight before the laboratory assessment will be considered.

Males:

$$\text{Creatinine CL} = \frac{\text{Weight(kg)} \times (140 - \text{Age})}{72 \times \text{serum creatinine (mg/dL)}}$$

Females:

$$\text{Creatinine CL} = \frac{\text{Weight}(kg) \times (140 - \text{Age})}{72 \times \text{serum creatinine (mg/dL)}} \times 0.85$$

Absolute values will be compared to the project reference range and classified as low (below range), normal (within range or on limits of range) and high (above range).

The maximum or minimum on-treatment value (depending on the direction of an adverse effect) will be defined for each laboratory parameter as the maximum (or minimum) post baseline value at any time.

Local reference ranges will be used for the primary interpretation of laboratory data at the local laboratory. Project reference ranges will be used throughout for reporting purposes.

The denominator used in laboratory summaries of CTCAE grades will only include evaluable patients, in other words those who had sufficient data to have the possibility of an abnormality.

For example:

- If a CTCAE criterion involves a change from baseline, evaluable patients would have both a baseline and at least 1 post-dose value recorded.
- If a CTCAE criterion does not consider changes from baseline, to be evaluable the patient need only have 1 post-baseline value recorded.

3.3.3 ECGs

Resting 12-lead ECGs are recorded at screening and as clinically indicated thereafter. Overall evaluation of ECG is collected in terms of normal, abnormal, or borderline, and the clinical relevance assessment for “abnormal” and “borderline” category is termed as “clinically significant” or “not clinically significant”.

In case of clinically significant ECG abnormalities, including a QT interval corrected for heart rate using Fridericia’s formula (QTcF) value >470 ms, 2 additional 12-lead ECGs should be obtained over a brief period (i.e., 30 minutes) to confirm the finding.

The QTcF will be derived during creating of the reporting database using the reported ECG values (RR and QT) using the following formula:

$$QTcF = \frac{QT}{RR^{\frac{1}{3}}} \quad \text{where RR is in seconds.}$$

ECG data obtained up until the safety follow-up (i.e. 30 days following last dose of the IP (durvalumab/placebo)) will be used for the reporting, and considered as “on-treatment”.

3.3.4 Vital signs

Vital signs data obtained between the date of first dose and up until the 30 days from date of last dose of IP will be used for reporting, and considered as “on-treatment”. Change from baseline in vital signs variables will be calculated for each post-dose visit on-treatment. For derivation of post baseline visit values considering visit window and to handle multiple records, derivation rules as described in [section 4.1.3](#) below will be used. The denominator in vital signs data should include only those patients with recorded data.

3.3.5 Study treatments

Study treatment in this study refers to durvalumab, and placebo. See [Table 8](#) for further details on the IPs. Exposure will be defined for durvalumab or placebo outlined below.

Table 8 Study treatments

	Study treatment name	Route of administration	Dosing instructions
Durvalumab	Durvalumab (MEDI4736)	IV	1500 mg IV q4w ^b
Placebo	Saline solution	IV	Saline volume matching durvalumab volume

^b If a patient’s weight falls to 30 kg or below, the patient should receive weight-based dosing equivalent to 20 mg/kg of durvalumab q4w until the weight improves to >30 kg, at which point the patient should start receiving the fixed dosing of durvalumab 1500 mg q4w.

IV Intravenous; q4w Every 4 weeks.

3.3.5.1 Treatment exposure for durvalumab or placebo

If a patient has a delay to receiving study treatment, all tumour efficacy assessments and PRO assessments should still be conducted relative to the date of randomisation.

Total (or intended) exposure of durvalumab (MEDI4736) or placebo

- Total (or intended) exposure = min (last dose date where dose>0mg+27 days, date of death, date of DCO) – first dose date +1

Actual exposure of durvalumab (MEDI4736) or placebo

- Actual exposure = intended exposure – total duration of dose delays, where intended exposure will be calculated as above.

Calculation of duration of dose delays (for actual exposure):

- Since patients will receive 1500 mg via intravenous (IV) infusion q4w, the duration of dose delays will be calculated as follows:

For all dosing dates:

Total duration of dose delays= Sum of (Date of the dose - Date of previous dose – 28 days)

Thus, if no delays were encountered, the duration would sum up to 0, since infusions were done every four weeks.

Dose reductions are not permitted per the CSP for durvalumab. The actual exposure calculation makes no adjustment for any dose reductions that may have occurred.

Patients who permanently discontinue during a dose delay

If a decision is made to permanently discontinue study treatment in-between cycles or during a dose delay, then the date of last administration of study medication recorded will be used in the programming.

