1 PROTOCOL SUMMARY

1.1 Schedule of activities (SoA)

The procedures for the Screening and Treatment Periods in this study are presented in Table 1, and the procedures for the Follow-up Period are presented in Table 2.

Whenever vital signs and blood draws are scheduled for the same nominal time, the assessments should occur in the following order: vital signs and then blood draws. The timing of the vital signs assessments should be such that it allows the blood draw (eg, pharmacokinetic (PK) blood sample) to occur at the timepoints indicated in the Schedule of Activities (SoAs). Whenever electrocardiograms (ECGs), vital signs, and blood draws are scheduled for the same nominal time, the assessments should occur in the following order: ECG, vital signs, and then blood draws. The timing of the first 2 assessments should be such that it allows the blood draw (eg, PK blood sample) to occur at the timepoints indicated in the SoAs. Safety assessments must be done prior to dosing.

For durvalumab monotherapy / placebo treatment

- Participants may delay dosing under certain circumstances.
 - Dosing may be delayed per the Dosing Modification and Toxicity Management Guidelines, due to either an immune or a non-immune-related adverse event (AE).
 - If dosing must be delayed for reasons other than treatment-related toxicity, dosing will resume as soon as feasible.
 - Dosing intervals of subsequent cycles may be shortened as clinically feasible in order to gradually align treatment cycles with the schedule of tumour efficacy (Response Evaluation Criteria in Solid Tumors [RECIST]) and patient-reported outcome (PRO) assessments. Subsequent time between 2 consecutive doses cannot be less than 21 days, based on the half-life of durvalumab (see current Investigator Brochure [IB] for durvalumab).
- If a participant has a delay to an infusion of study treatment, all tumour efficacy assessments should still be conducted relative to date of randomisation, and PRO assessments should be conducted relative to the date of Cycle 1 Day 1 visit date (i.e. date of randomization/first dose).

Table 1Schedule of activities for durvalumab/placebo treatment

	Screening Visit Part I	Screening Visit Part II	C1	C2	C3	C4	C5 to PD	
Week	-12 to -1	-4 to -1	0	q4w ±3	3 days unless dos	sing needs to be h	eld for toxicity reasons	For details,
Day	-84 to -1	-28 to -1	1 ^b	q28d ±.	3 days unless do	sing needs to be l	held for toxicity reasons	see Section
Informed consent								·

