4.2.12 Treatment exposure and intensity

The following summaries related to study treatment will be produced for the safety analysis set by treatment group:

- Total exposure
- Actual exposure (durvalumab or matching placebo only)

- Reasons for dose delays/interruptions. Dose interruptions will be based on investigator initiated dosing decisions
- Number of infusions received
- Relative dose intensity (RDI) (durvalumab or matching placebo only)
- Cumulative exposure over time

For patients on study treatment at the time of the IA, the DCO date will be used to calculate exposure.

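### SAP 3.3.5.1 nets early infusions against late ones, so dose delay can be negative and a hold vanishes to the extent that later doses catch up

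*SAP*

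**What the plan says.** SAP 3.3.5.1 gives three linked definitions.

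- Total exposure: "Total (or intended) exposure = min (last dose date where dose>0mg+27 days, date of death, date of DCO) – first dose date +1".
- Actual exposure: "Actual exposure = intended exposure – total duration of dose delays".
- Delay, over all dosing dates: "Total duration of dose delays= Sum of (Date of the dose - Date of previous dose – 28 days".

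It then offers a check on the delay formula: "Thus, if no delays were encountered, the duration would sum up to 0, since infusions were done every four weeks". It states no floor at zero and no rule for an interval shorter than 28 days.

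The protocol permits such intervals in two ways. Table 1 and Figure 2 schedule dosing every 28 days ±3 days. For the period after a delay, Protocol 1.1 says: "Dosing intervals of subsequent cycles may be shortened as clinically feasible in order to gradually align treatment cycles", subject to a lower limit: "Subsequent time between 2 consecutive doses cannot be less than 21 days".

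SAP 4.2.12 lists total exposure, actual exposure, number of infusions, relative dose intensity and "Reasons for dose delays/interruptions. Dose interruptions will be based on investigator initiated dosing decisions". It ends with a separate sentence on cut-off: "For patients on study treatment at the time of the IA, the DCO date will be used to calculate exposure".

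**The concern.** A quantity called the total duration of dose delays should not fall below zero, and exposure net of delays should not exceed exposure before they are removed. The formula allows both under dosing that the protocol permits. It also lets a hold and the later catch-up offset each other, so a patient who was off drug for some weeks and then realigned can be reported with no delay.

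The gap between total and actual exposure is the only place where the SAP derives how long dosing was delayed, and Protocol 9.5.2 commits to summarising dose delays in both arms. A reader of the clinical study report would take that gap as time lost to holds. As written, it is time lost minus time recouped, and it carries little information beyond the infusion count already in the same list.

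**Working it through.** **Inputs.** Total exposure, delay and actual exposure as defined in SAP 3.3.5.1; the ±3-day window (Protocol Table 1 and Figure 2); the 21-day minimum (Protocol 1.1). Let F and L be the first and last dose dates and n the number of infusions. The dates summed are taken to be those of non-zero doses. The SAP says all dosing dates for the sum but restricts the last dose to doses above 0 mg.

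**The SAP's own check.** Nine doses exactly 28 days apart: L − F = 224, total = 224 + 28 = 252, delay = 224 − 28 × 8 = 0, actual = 252. The stated zero reproduces when every interval is exactly 28 days.

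**Algebra.** The signed sum telescopes, so the intermediate dates drop out:

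- delay = (L − F) − 28(n − 1)
- total, untruncated = (L + 27) − F + 1 = (L − F) + 28
- actual = total − delay = 28 + 28(n − 1) = 28n

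If death or DCO falls k days after the last dose (k < 27), total = (L − F) + k + 1 and actual = 28(n − 1) + k + 1. The value is no longer 28n, but early and late doses still cancel.

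**Schedules, in days.** The floored columns replace each term by max(0, interval − 28).

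| Schedule | n | L − F | Total | Delay, SAP | Actual, SAP | Delay, floored | Actual, floored |
|---|---|---|---|---|---|---|---|
| Patient 3 in the SAP 3.3.6 example (days 1, 29, 57, 113, 141) | 5 | 140 | 168 | 28 | 140 | 28 | 140 |
| No hold, only the last dose 3 days early | 13 | 333 | 361 | −3 | 364 | 0 | 361 |
| No hold, every interval 25 days | 13 | 300 | 328 | −36 | 364 | 0 | 328 |
| 14-day hold, then two 21-day intervals | 10 | 252 | 280 | 0 | 280 | 14 | 266 |
| 28-day hold, then four 21-day intervals | 12 | 308 | 336 | 0 | 336 | 28 | 308 |
| 28-day hold, no catch-up | 12 | 336 | 364 | 28 | 336 | 28 | 336 |
| 56-day hold, then eight 21-day intervals | 13 | 336 | 364 | 0 | 364 | 56 | 308 |

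Intervals not described are 28 days.

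**Range without holds.** The second and third rows bracket the effect for 13 infusions. If the window is fixed to a grid (days 1, 29, 57 and so on), in-window variation cannot accumulate and actual exceeds total by at most 3 days (3/361, under 1%). If it runs from the previous dose, twelve intervals of 25 days are all in window and the excess reaches 36 days (36/328, 11%). The documents do not state the anchor.

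**Whether another table shows the length.** In the 14-day hold case, 10 doses are given by day 253, the nominal day of the tenth dose. Relative dose intensity under SAP 3.3.6 is therefore 10/10 = 100%. The infusion count is 10. The planned tables of reasons for delay and of adverse events leading to dose delay (SAP 4.2.12 and 4.2.5.1) show that a delay occurred, not how long it lasted.

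**The case against.** The best defence is that a signed sum has a meaning: net delay. A patient with a 56-day hold, fully recouped, received 13 infusions in 364 days, and reporting 364 days agrees with the doses delivered. The floored rule reports 308 days, the equivalent of 11 cycles. Gross or net is a matter of definition, and the sentence on summing to zero states its own premise of four-weekly infusions.

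Part of this stands. Net delay could be reported if it were named as such. It does not fit a variable labelled total duration of dose delays that can go below zero, and the premise of exact four-weekly dosing is not the schedule the protocol allows.

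Several stronger readings are tempting, and the documents do not support them.

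- **Holds are hidden altogether.** They are not. A hold without catch-up is counted in full (Patient 3: 28 days), partial catch-up hides only part, and other tables record that delays occurred.
- **Early dosing inflates exposure by 11%.** That holds only if the window runs from the previous dose and every interval is at its lower edge. The dosing days in the SAP 3.3.6 example and the visit windows in SAP 4.1.3 fit a fixed grid at least as well.
- **Actual exposure is always 28n.** This fails when death or DCO comes within 27 days of the last dose, as it may for many patients on treatment at a cut-off.
- **The comparison of delay between arms is biased.** The documents give no rates of holds or catch-up by arm, so neither direction nor size can be stated.
- **SAP 4.2.12 contradicts 3.3.5.1.** DCO is already a term in the minimum, and the 4.2.12 sentence can be read as shorthand for it. The two differ only for a patient still on treatment whose last dose plus 27 days falls before DCO.

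**Conclusion.** The formula is wrong as written. Applied literally to permitted dosing, it can return a negative delay, an actual exposure above total exposure, and zero delay after a fully recouped hold. The algebra is exact and needs only that the summed dates are non-zero doses. How far it matters depends on facts the documents do not give: how often intervals fall below 28 days, and what the ±3-day window is measured from.

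The consequence is confined to descriptive exposure summaries. No test, estimate or alpha allocation for PFS or OS uses these variables. It is a modest correction, worth making before the exposure tables are programmed.

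**What to change.** In SAP 3.3.5.1, define total duration of dose delays as the sum over doses of max(0, date of dose − date of previous dose − 28). Actual exposure can then never exceed total.

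If in-window lateness should not count, put the allowance inside the maximum: max(0, interval − 31). A rule that counts the full excess over 28 once an interval passes 31 days would jump from 0 at 31 days to 4 at 32 days.

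Reword the sentence on summing to zero: the sum is 0 when no interval exceeds 28 days (or 31, if the allowance is used). In SAP 4.2.12, state that DCO enters only through the minimum in 3.3.5.1.

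The cost is one formula and two sentences, with no change to data collection or dosing. Actual exposure becomes shorter for patients who were held and then caught up: for the 56-day hold over 13 doses, 308 rather than 364 days, or 364 − (84 − 31) = 311 with the allowance. Without the allowance, small in-window lateness counts as delay: 13 doses at alternating 31- and 25-day intervals give 6 × 3 = 18 days, against 0 with it. Even with it, a dose 3 days early on a fixed grid followed by one 3 days late makes a 34-day interval and counts 34 − 31 = 3 days. The authors should choose one form and say so.
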